5.3.5.8 Preexisting Medical Conditions

A preexisting medical condition is one that is present at the screening visit for this study. Such conditions should be recorded on the General Medical History and Baseline Conditions eCRF.

A preexisting medical condition should be recorded as an adverse event only if the frequency, severity, or character of the condition worsens during the study. When

recording such events on the Adverse Event eCRF and source form, it is important to convey the concept that the preexisting condition has changed by including applicable descriptors (e.g., "more frequent headaches").

5.3.5.9 Hospitalization or Prolonged Hospitalization

Any AE that results in hospitalization (i.e., inpatient admission to a hospital) or prolonged hospitalization should be documented and reported as a serious adverse event (per the definition of serious adverse event in Section [5.2.2](#)), except as outlined below.

An event that leads to hospitalization under the following circumstances should not be reported as an AE or a SAE:

- Hospitalization for respite care
- Planned hospitalization required by the protocol
- Hospitalization for a preexisting condition, provided that all of the following criteria are met:
 - The hospitalization was planned prior to the study or was scheduled during the study when elective surgery became necessary because of the expected normal progression of the disease
 - The subject has not experienced an AE

An event that leads to hospitalization under the following circumstances is not considered to be a SAE, but should be reported as an AE instead:

- Hospitalization that was necessary because of subject requirement for outpatient care outside of normal outpatient clinic operating hours

5.4 IMMEDIATE REPORTING REQUIREMENTS FROM INVESTIGATOR TO SPONSOR

Certain events require immediate reporting to allow the Sponsor to take appropriate measures to address potential new risks in a clinical trial. The Investigator or designee must report such events to the Sponsor immediately; under no circumstances should reporting take place more than 24 hours after the Investigator or designee learns of the event. The following is a list of events that the Investigator or designee must report to the Sponsor within 24 hours after learning of the event, regardless of relationship to study drug:

- Serious adverse events (defined in Section [5.2.2](#); see Section [5.4.2](#) for details on reporting requirements)
- Adverse events of special interest (defined in Section [5.2.3](#); see Section [5.4.2](#) for details on reporting requirements)
- Pregnancies (see Section [5.4.3](#) for details on reporting requirements)

The Investigator or designee must report new significant follow-up information for these events to the Sponsor immediately (i.e., no more than 24 hours after becoming aware of the information). New significant information includes the following:

- New signs or symptoms or a change in the diagnosis
- Significant new diagnostic test results
- Change in causality based on new information
- Change in the event's outcome, including recovery
- Additional narrative information on the clinical course of the event

Investigator or designees must also comply with local requirements for reporting serious adverse events to the local health authority and IRB/EC.

5.4.2 Reporting Requirements for Serious Adverse Events and Adverse Events of Special Interest

5.4.2.1 Events That Occur prior to Study Drug Initiation

After informed consent has been obtained but prior to initiation of study drug, only serious adverse events caused by a protocol-mandated intervention should be reported. The paper Clinical Trial Serious Adverse Event (SAE)/AE of Special Interest Reporting Form provided to Investigator or designees should be completed and submitted to the Sponsor or its designee immediately (i.e., no more than 24 hours after learning of the event), either by faxing or by scanning and emailing the form using the fax number or email address provided to Investigator.

5.4.2.2 Events That Occur after Study Drug Initiation

After initiation of study drug, SAEs and AEs of special interest will be reported until 21 days after the last dose of study drug. Investigator or designees should record all case details that can be gathered immediately (i.e., within 24 hours after learning of the event) on the paper Clinical Trial Serious Adverse Event/Adverse Event of Special Interest Reporting Form provided to investigators and submitting the report, either by faxing or by scanning and emailing the form using the fax number or email address provided to investigators.

Instructions for reporting SAEs that occur >21 days after the last dose of study treatment are provided in Section [5.6](#).

5.4.3 Reporting Requirements for Pregnancies

5.4.3.1 Pregnancies in Female Subjects

Female subjects of childbearing potential will be instructed to immediately inform the Investigator or designee if they become pregnant during the study or within 90 days after the last dose of study drug. A paper Clinical Trial Pregnancy Reporting Form should be completed and submitted to the Sponsor or its designee immediately (i.e., no more than 24 hours after learning of the pregnancy), either by faxing or by scanning and emailing the form using the fax number or email address provided to the Investigator. Pregnancy should not be recorded on the Adverse Event eCRF and source form. The Investigator or designee should discontinue the study drug and counsel the subject, discussing the risks of the pregnancy and the possible effects on the fetus. Monitoring of the subject should continue until conclusion of the pregnancy. Any SAE associated with the pregnancy (e.g., an event in the fetus, an event in the mother during or after the pregnancy, or a congenital anomaly/birth defect in the child) should be reported on the Adverse Event eCRF and source form. In addition, the Investigator or designee will submit a Clinical Trial Pregnancy Reporting Form when updated information on the course and outcome of the pregnancy becomes available.

5.4.3.2 Pregnancies in Female Partners of Male Subjects

Male subjects will be instructed through the Informed Consent Form to immediately inform the Investigator or designee if their partner becomes pregnant during the study or within 90 days after the last dose of study drug. A paper Clinical Trial Pregnancy Reporting Form should be completed and submitted to the Sponsor or its designee immediately (i.e., no more than 24 hours after learning of the pregnancy), either by faxing or by scanning and emailing the form using the fax number or email address provided to investigators. Attempts should be made to collect and report details of the course and outcome of any pregnancy in the partner of a male subject exposed to study drug. When permitted by the site, the pregnant partner would need to sign an Authorization for Use and Disclosure of Pregnancy Health Information to allow for follow-up on her pregnancy. If the authorization has been signed, the Investigator or designee should submit a Clinical Trial Pregnancy Reporting Form when updated information on the course and outcome of the pregnancy becomes available. An

Investigator or designee who is contacted by the male subject or his pregnant partner may provide information on the risks of the pregnancy and the possible effects on the fetus, to support an informed decision in cooperation with the treating physician and/or obstetrician.

5.4.3.3 Abortions

Any abortion should be classified as a SAE (as the Sponsor considers abortions to be medically significant), recorded on the Adverse Event eCRF and source form, and reported to the Sponsor immediately (i.e., no more than 24 hours after learning of the event; see Section 5.4.2).

5.4.3.4 Congenital Anomalies/Birth Defects

Any congenital anomaly/birth defect in a child born to a female subject exposed to study drug or the female partner of a male subject exposed to study drug should be classified as a serious adverse event, recorded on the Adverse Event form, and reported to the Sponsor immediately (i.e., no more than 24 hours after learning of the event; see Section 5.4.2).

5.4.4 Reporting Requirements for Cases of Accidental Overdose or Medication Error

Accidental overdose and medication error (hereafter collectively referred to as "special situations"), are defined as follows:

- Accidental overdose: accidental administration of a drug in a quantity that is higher than the assigned dose
- Medication error: accidental deviation in the administration of a drug

In some cases, a medication error may be intercepted prior to administration of the drug.

Special situations are not in themselves adverse events but may result in adverse events. Each adverse event associated with a special situation should be recorded separately on the Adverse Event eCRF. If the associated adverse event fulfills seriousness criteria, the event should be reported to the Sponsor immediately (i.e., no more than 24 hours after learning of the event; see Section 5.4.2) Special situations should be recorded as described below:

- Accidental overdose: Enter the drug name and "accidental overdose" as the event term. Check the "Accidental overdose" and "Medication error" boxes.
- Medication error that does not qualify as an overdose: Enter the name of the drug administered and a description of the error (e.g., wrong dose administered, wrong dosing schedule, incorrect route of administration, wrong drug, expired drug administered) as the event term. Check the "Medication error" box.
- Medication error that qualifies as an overdose: Enter the drug name and "accidental overdose" as the event term. Check the "Accidental overdose" and "Medication error" boxes. Enter a description of the error in the additional case details.

- Intercepted medication error: Enter the drug name and "intercepted medication error" as the event term. Check the "Medication error" box. Enter a description of the error in the additional case details.

For study drug, each AE associated with a special situation should be recorded separately on the Adverse Event eCRF and source form. If the associated AE fulfills seriousness criteria, the event should be reported to the Sponsor immediately (i.e., no more than 24 hours after learning of the event; see Section 5.4.2). Study drug AEs associated with special situations should be recorded as described below for each situation:

- Accidental overdose: Enter the adverse event term. Check the "Accidental overdose" and "Medication error" boxes.
- Medication error that does not qualify as an overdose: Enter the adverse event term. Check the "Medication error" box.
- Medication error that qualifies as an overdose: Enter the adverse event term. Check the "Accidental overdose" and "Medication error" boxes.

As an example, an accidental overdose that resulted in a headache would require the completion of two Adverse Event eCRF and source form, one to report the accidental overdose and one to report the headache. The "Accidental overdose" and "Medication error" boxes would need to be checked on both eCRF pages.

5.5 FOLLOW-UP OF SUBJECTS AFTER ADVERSE EVENTS

5.5.1 Investigator Follow-Up

The Investigator or designee should follow each adverse event until the event has resolved to baseline grade or better, the event is assessed as stable by the Investigator or designee, the subject is lost to follow-up, or the subject withdraws consent. Every effort should be made to follow all SAEs considered to be related to study drug or trial-related procedures until a final outcome can be reported.

During the study period, resolution of adverse events (with dates) should be documented on the Adverse Event eCRF and source form and in the subject's medical record to facilitate source data verification.

All pregnancies reported during the study should be followed until pregnancy outcome.

5.5.2 Sponsor Follow-Up

For SAEs, AESI, and pregnancies, the Sponsor or a designee may follow up by telephone, fax, email, and/or a monitoring visit to obtain additional case details and outcome information (e.g., from hospital discharge summaries, consultant reports, autopsy reports) in order to perform an independent medical assessment of the reported case.

5.6 ADVERSE EVENTS THAT OCCUR AFTER THE ADVERSE EVENT REPORTING PERIOD

The Sponsor should be notified if the Investigator or designee becomes aware of any SAE that occurs after the end of the AE reporting period (defined as 21 days after the last dose of study drug), if the event is believed to be related to prior study drug treatment. These events should be reported through use of the Adverse Event eCRF and source form. The Investigator or designee should report these events directly to the Sponsor or its designee, either by faxing or by scanning and emailing the paper Clinical Trial Serious Adverse Event/Adverse Event of Special Interest Reporting Form using the fax number or email address provided to investigators.

5.7 EXPEDITED REPORTING TO HEALTH AUTHORITIES, INVESTIGATORS, INSTITUTIONAL REVIEW BOARDS, AND ETHICS COMMITTEES

The Sponsor will promptly evaluate all SAEs and AESI against cumulative product experience to identify and expeditiously communicate possible new safety findings to Investigator (or designee), IRBs, ECs, and applicable health authorities based on applicable legislation.

Independent from the causality assessment, the following SAEs and non-SAEs of special interest will be reported to the FDA on an expedited basis: death, arrhythmia, syncope, dyspnea, palpitations, and chest pain.

To determine reporting requirements for single AE cases, the Sponsor will assess the expectedness of these events using the following reference documents:

- RO5285119 (Balovaptan) Investigator's Brochure
- Moxifloxacin package insert as relevant in the United States of America

The Sponsor will compare the severity of each event and the cumulative event frequency reported for the study with the severity and frequency reported in the applicable reference document.

Reporting requirements will also be based on the Investigator or designee's assessment of causality and seriousness, with allowance for upgrading by the Sponsor as needed.

An aggregate report of any clinically relevant imbalances that do not favor the test product will be submitted to health authorities.

6. STATISTICAL CONSIDERATIONS AND ANALYSIS PLAN

A statistical analysis plan (SAP) will be generated by the biostatistics department of the Sponsor and will be finalized prior to database lock.

6.1 DETERMINATION OF SAMPLE SIZE

A sample size of 56 subjects was chosen to obtain 48 evaluable subjects. Subjects are evaluable if ECGs are available for all three periods to allow (1) the derivation of the primary endpoint (i.e., change from baseline on Day 14), and (2) the assessment of the effect of moxifloxacin.

Based on the calculation of the sample size for a TQT study (Zhang and Machado, 2008)⁶, assuming a 1-sided 5% significance level and a within-subject SD of 8 ms for $\Delta QTcF$ and a true mean difference of 3 ms in $\Delta QTcF$ between balovaptan and placebo, a sample size of 48 evaluable subjects who complete the study will provide a power of 96.6% to demonstrate that the upper bound of all the 2-sided 90% CIs on $\Delta\Delta QTcF$ will fall below 10 ms for up to 7 post-dose time points (0.5, 1.25, 2.5, 4, 8, 12 and 24 hours).

Sample Size Determination for Assay Sensitivity:

Based on the calculation of the sample size for a TQT study from Zhang and Machado, 2008⁶, as the test is performed at three time points separately (1.25, 2.5, and 4 hours), a one-sided 5% significance level (with adjusted one-sided significance levels of 5%, 2.5% and 1.67%) is used along with a within-subject SD of 8 ms for $\Delta QTcF$, a sample size of 48 evaluable subjects who complete the study will provide a power of 99% to prove a mean difference of 5 ms in $\Delta QTcF$ between moxifloxacin and placebo (i.e., $\Delta\Delta QTcF$) at $1 \geq$ of the 3 specified time points.

6.2 SUMMARIES OF CONDUCT OF STUDY

The number of subjects who enroll, discontinue, or complete the study will be summarized. Reasons for premature study withdrawal will be listed and summarized. Enrollment and major protocol deviations will be listed and evaluated for their potential effects on the interpretation of study results.

6.3 SUMMARIES OF DEMOGRAPHIC AND BASELINE CHARACTERISTICS

Demographic and baseline characteristics (including age, sex) will be summarized using means, standard deviations, medians, and ranges for continuous variables and proportions for categorical variables, as appropriate. Summaries will be presented overall and by treatment group.

6.4 EFFICACY ANALYSES

Not Applicable

6.5 SAFETY ANALYSES

All subjects who have received at least one dose of balovaptan, whether prematurely withdrawn from the study or not, will be included in the safety analysis. The safety data, including AEs, laboratory data, and vital signs, will be listed and summarized by study treatment. Reasons for withdrawal from study will be listed and summarized.

Concomitant medications, 12-lead ECG data and clinically significant neurological examinations will be listed. Adverse events will be listed and summarized by treatment, body system and preferred term using the Medical Dictionary for Regulatory Activities (MedDRA). All verbatim AE terms will be mapped to MedDRA thesaurus terms, and AE severity will be graded according to [Table 3](#). For laboratory and 12-lead ECG data, subject listings will be presented with abnormalities flagged.

For statistical analyses of results from TT-Doppler echocardiogram and ABPM please see Sections [6.8](#) and [6.9](#) below.

6.6 PHARMACOKINETIC ANALYSES

Subjects will be excluded from the PK analysis population if they significantly violate the inclusion or exclusion criteria, deviate significantly from the protocol, or if data are unavailable or incomplete. Excluded cases will be documented together with the reason for exclusion. All decisions on exclusions from the analysis will be made prior to database closure.

Pharmacokinetics are a secondary objective of this study. The specific objectives are

- To investigate the pharmacokinetics of balovaptan, M2 (as appropriate), and M3.
- To investigate the pharmacokinetics of moxifloxacin.

Individual plasma concentrations at each sampling timepoint for balovaptan, M2 (as appropriate), M3, and moxifloxacin will be presented by listings and descriptive summary statistics by treatment, including means, geometric means, ranges, standard deviations and coefficients of variation. Individual and mean concentration versus time will be plotted on linear and semi-logarithmic scales.

PK parameters will be estimated using standard non-compartmental methods. All PK parameters for balovaptan, M2 (as appropriate), and M3 will be presented by individual listings and summary statistics by treatment including means, geometric means, medians, ranges, standard deviations and coefficients of variation.

The following balovaptan, M2 (as appropriate), M3 PK parameters will be estimated:

- Cmax: Day 1 and Day 14 for Treatment A and B
- AUC0-24h: Day 1 and Day 14 for Treatment A and B
- Tmax: Day 1 and Day 14 for Treatment A and B
- Ctrough: Day 11, 12, 13, 14 for Treatment A and B
- Time to steady state for Treatment A and B

The following moxifloxacin PK parameters will be estimated:

- Cmax, AUC0-24h, and Tmax will be estimated on Days 2 (Treatment C) or 15 (Treatment D)

Additional PK analyses maybe be conducted as appropriate for balovaptan, M2 (as appropriate), M3 and moxifloxacin.

Subjects will be excluded from the PK analysis population if they significantly violate the inclusion or exclusion criteria, deviate significantly from the protocol, or if data are unavailable or incomplete. Excluded cases will be documented together with the reason for exclusion. All decisions on exclusions from the analysis will be made prior to database closure.

6.7 CARDIODYNAMIC ECG EVALUTAION

The following ECG parameters will be measured and calculated: HR, PR, QT, QTcF, and QRS. T-wave morphology and U-wave presence will be assessed.

The primary analysis will be based on by-time point analysis to evaluate the effect of balovaptan on the placebo-corrected change-from-baseline QTcF ($\Delta\Delta QTcF$) at each post-dosing time point using the Intersection Union Test. The effect of balovaptan on placebo-corrected change-from-baseline in HR, PR, and QRS ($\Delta\Delta HR$, $\Delta\Delta PR$, and $\Delta\Delta QRS$) will also be evaluated using the Intersection Union Test. In addition, the relationship between plasma concentrations of balovaptan and its metabolites (M2 [as appropriate] and M3) and $\Delta\Delta QTcF$ will be evaluated using a linear mixed-effects modeling approach. An analysis of categorical outliers will be performed for changes in HR, PR, QRS, QTcF, T-wave morphology and U-wave presence. Assay sensitivity will also be evaluated using by-time point analysis of the effect on $\Delta\Delta QTcF$ of moxifloxacin using a similar model as for the primary analysis.

6.7.1 Analysis Populations

The Safety population will include all subjects who are randomized and received at least one dose of the study medication (either balovaptan, moxifloxacin or matching placebo), whether prematurely withdrawn from the study or not.

The PK population will include all subjects who receive at least 1 dose of investigational product and have at least 1 evaluable PK plasma concentration of balovaptan (and moxifloxacin, when applicable).

The QT/QTc population will include all subjects in the Safety population with measurements at baseline as well as on-treatment with at least 1 post-dose time point with a valid $\Delta QTcF$ value. The QT/QTc population will be used for the by-time point and categorical analyses of cardiodynamic ECG parameters.

The PK/QTc population will include all subjects who are in both the QT/QTc and PK populations with at least 1 pair of post-dose PK and QTcF data from the same time point. The PK/QTc population will be used for the concentration-QTc analysis. PK/QTc population will be defined for balovaptan (and for moxifloxacin, when applicable).

6.7.3 By-Time Point Analysis

The statistical hypothesis to be tested for the primary assessment of QT prolongation for each dose of the balovaptan treatment is:

$$H_0: \cup \{\mu_{D(i)} - \mu_{P(i)}\} \geq 10, i = 1, 2, \dots, 7$$

$$H_1: \cap \{\mu_{D(i)} - \mu_{P(i)}\} < 10, i = 1, 2, \dots, 7$$

where $\mu_{D(i)}$ and $\mu_{P(i)}$ are the least squares (LS) mean of Δ QTcF for each dose of balovaptan and placebo at time point i on Day 14, respectively.

The “by-time point” analysis for QTcF will be based on a linear mixed-effects model with change-from-baseline QTcF (Δ QTcF) as the dependent variable; gender, period, sequence, time (categorical), treatment (balovaptan, and placebo), and time-by-treatment interaction as fixed effects; and baseline QTcF as a covariate. An unstructured covariance matrix will be specified for the repeated measures at time points for subject within treatment period. If the model with an unstructured covariance matrix fails to converge, other covariance matrices such as compound symmetry and autoregressive will be considered. If the fixed effects for period and/or sequence should prove to be nonsignificant (i.e., if the p value > 0.1), these effects may be removed from the model.

and the analysis will be repeated without those covariates. From this analysis, the LS mean and 2-sided 90 % CI will be calculated for the contrast “balovaptan versus placebo” at each dose of balovaptan and each post-dose time point on Day 1 and Day 14, separately. If the upper bound of the CI lies below 10 ms for the highest dose group of balovaptan at all seven post-dose time points (0.5, 1.25, 2.5, 4, 8, 12, and 24 hours) on Day 14 (steady state), balovaptan will be concluded not to have a significant effect on QT interval prolongation.

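### The primary QTcF model in Protocol 6.7.3 states no link between a subject's periods, although 6.1 sizes a paired comparison; the same model cannot be applied unchanged to the moxifloxacin data in 6.7.5

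*Protocol*

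**What the plan says.** Under Protocol 6.7.3 the by-time-point analysis "will be based on a linear mixed-effects model with change-from-baseline QTcF" as the outcome. The fixed terms are sex, period, sequence, categorical time, treatment and time by treatment, with baseline QTcF as a covariate. On covariance it says: "An unstructured covariance matrix will be specified for the repeated measures at time points for subject within treatment period". If that fails to converge, "other covariance matrices such as compound symmetry and autoregressive will be considered". A further rule begins "If the fixed effects for period and/or sequence should prove to be nonsignificant" (p above 0.1) and allows those terms to be dropped. No random subject term and no covariance between a subject's periods is stated. Section 6.7.4 reuses the model for HR, PR and QRS. By contrast, 6.7.7 does name subject as a random effect for the concentration-QTc model.

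On sizing, Protocol 6.1 says: "A sample size of 56 subjects was chosen to obtain 48 evaluable subjects". It adds: "Subjects are evaluable if ECGs are available for all three periods". The calculation assumes "a 1-sided 5% significance level and a within-subject SD of 8 ms" for change from baseline, with a true difference of 3 ms, and gives 96.6% power over seven time points. The analysis set is wider than the evaluable subjects. Section 6.7.1 says: "The QT/QTc population will be used for the by-time point and categorical analyses of cardiodynamic ECG parameters", and that population needs only a baseline and one valid post-dose value.

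For assay sensitivity, 6.7.5 reuses the primary model (6.7 calls it a similar one). Sections 3.3.1.2 and 6.7.2 take moxifloxacin and placebo from a single joint period: Days 2 and 14 in Treatment C, Days 15 and 1 in Treatment D.

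SAP 5.0 leaves the cardiodynamic ECG analysis to a separate SAP by ERT, which is not among the documents.

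**The concern.** The value of a crossover lies in removing stable differences between subjects from the treatment contrast. The 6.1 sizing relies on this. The covariance statement in 6.7.3 stops at subject within period, and its fallbacks change the structure of that block without joining the periods. Such a model runs without any error message. If a subject's changes correlate across periods, it leaves between-subject variance in the standard error of balovaptan minus placebo. The primary rule, that all seven upper 90% bounds on Day 14 lie below 10 ms, rests on those standard errors.

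The moxifloxacin data have a different shape: two days in one period for each subject. A model built for one day per period does not say how to handle them, and assay sensitivity rests on that contrast.

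**Working it through.** **1. Reproduce the 96.6%.** Inputs from 6.1: SD 8 ms, n = 48, margin 10 ms, true difference 3 ms, one-sided 5%, seven time points.

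- SE = 8 × √(2/48) = 1.633 ms
- Noncentrality = (10 − 3)/1.633 = 4.287 on 47 df, giving power 0.99505 per time point
- 0.99505^7 = 0.9658, the stated 96.6%

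Parallel-group readings do not fit: 24 per arm gives 51.8% and 28 per arm gives 66.4%. The sizing is paired.

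**2. Primary contrast under a literal fit.** Let ρ be the between-period correlation of baseline-adjusted change. The documents give no value, so 0.2, 0.3 and 0.5 are assumptions. The within-subject variance stays at 64 and the between-subject variance is 64ρ/(1 − ρ).

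Take one time point, 48 complete subjects, 12 sequences and 3 periods, leaving out sex and baseline. There are 144 records. Intercept plus sequence use 12 df, period 2 and treatment 2, which leaves 128. Sequence absorbs 12 of the 48 subject dimensions. The other 36, with 3 records each, contribute 108:

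- residual variance s² = 64 + [64ρ/(1 − ρ)] × 108/128
- reported SE = √(2s²/48)
- half-width = 1.657 × reported SE (t on 128 df)
- seven-point power = Φ((7 − half-width)/1.633)^7, time points independent
- one-sided error at a true 10 ms = Φ(−half-width/1.633)

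The true sampling SD of the contrast remains 1.633 ms, because the design is balanced.

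| ρ | s² | Reported SE (ms) | Half-width (ms) | Seven-point power | Error at 10 ms |
|---|---|---|---|---|---|
| 0 | 64.0 | 1.63 | 2.71 | 97.0% | 4.9% |
| 0.2 | 77.5 | 1.80 | 2.98 | 95.3% | 3.4% |
| 0.3 | 87.1 | 1.91 | 3.16 | 93.7% | 2.7% |
| 0.5 | 118.0 | 2.22 | 3.67 | 86.3% | 1.2% |

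The first row differs slightly from 96.6% because it uses 128 df and treats the SE as known.

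**3. The 6.7.5 data.**

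- *Block.* Each subject-period holds 2 days × 7 times = 14 records on 7 time levels. A matrix indexed by time point alone has rank 7 of 14 and is singular. Indexed by day and time, the unstructured matrix has full rank 14 and lets within-day and between-day correlation differ.
- *Period.* Each subject contributes one period, which the sequence determines. Intercept plus sequence has rank 12, and adding period leaves it at 12. The p > 0.1 rule has nothing to test for period.
- *Treatment levels.* Section 6.7.3 lists balovaptan and placebo, not moxifloxacin.

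**4. Compound symmetry by record, if it were reached.** Of the 91 pairs in a block, 42 lie within a day and 49 between days. The fitted correlation is (42·r_within + 49·r_between)/91, and the ratio of reported to true SE is √((1 − r_fitted)/(1 − r_between)). For assumed (0.5, 0.3): r_fitted = (21 + 14.7)/91 = 0.392, ratio √(0.608/0.7) = 0.93. For (0.7, 0.1): r_fitted = (29.4 + 4.9)/91 = 0.377, ratio √(0.623/0.9) = 0.83. Simulation (40,000 runs, n = 48, three time points, Hochberg) over five assumed pairs, with within-day correlation 0.5 to 0.7 and between-day 0.1 to 0.5, gives a false-positive rate at a true 5 ms of 6.4 to 8.7%. The paired variance gives 4.1 to 4.7%. With both correlations at 0.3 there is no distortion (4.9%).

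**The case against.** The strongest reply is that 6.7.3 calls the model mixed-effects, which suggests that a random term is intended, and that SAP 5.0 sends the detail to the ERT SAP. Both are fair and limit the point to the protocol text. They do not supply the missing term: the label does not say which effect is random, and 6.7.7 shows that the protocol writes a subject effect where it wants one.

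A second reply concerns size, and much of it stands. The fixed sequence effect absorbs part of the between-subject variance. The shortcut 1.633/√(1 − ρ) ignores this and would give 2.31 ms and 83.8% at ρ = 0.5, which overstates the loss. Baseline adjustment may also keep ρ low. Correlated time points and a larger analysis set soften the loss further. Even with the shortcut, time points correlated 0.7 give 97.0, 95.9 and 91.1% (98.2% at ρ = 0). If all 56 enrolled subjects contribute, independent time points give 98.2, 97.3 and 92.8% (99.0% at ρ = 0).

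A third reply concerns 6.7.5. A reader might infer that the planned assay-sensitivity test has an error rate of 6 to 9%. The documents do not support that. The figure needs three things together: the unstructured fit fails, compound symmetry by record replaces it, and within-day correlation exceeds between-day. Indexed by day and time, the first-choice matrix gives the right SE: over 2,000 simulated data sets at each of three correlation pairs the mean was 1.626 to 1.634 ms, against a true 1.633. If the block is instead each treatment day separately, positive between-day correlation makes the SE too large, so assay sensitivity becomes harder to show. Indexing by time point alone fails visibly at fitting. The period aliasing does not disturb the moxifloxacin contrast, which lies within one period.

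**Conclusion.** The point holds for the protocol as written. Section 6.7.3 leaves out the between-period link on which the 6.1 sizing depends. A literal fit gives primary standard errors that are too large if ρ is positive. With 48 complete subjects and independent time points, the cost is about 2, 3 and 11 points of seven-point power at assumed ρ of 0.2, 0.3 and 0.5. No document supports a particular ρ.

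A reader might infer that the omission could let a QT effect pass unnoticed. It could not: under positive correlation the intervals widen and the error at 10 ms falls below 5%. Nor do the documents show that the periods will in fact be analysed as independent, since the ERT SAP was not supplied.

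The 6.7.5 mismatch is secondary. It is a certain gap in the text, but one that would show at fitting. It should be fixed, with medium confidence, because the correction is specific and nearly free.

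**What to change.** - **6.7.3, and so 6.7.4:** name subject as a random effect, or specify a covariance spanning a subject's periods. Keep the unstructured matrix within subject-period, and state a random subject intercept as the fallback.
- **6.7.5:** state the treatment levels as moxifloxacin and placebo. Index the repeated block by treatment day and time, with a subject link between the two days. Keep period or sequence, not both. If a fallback is needed, let within-day and between-day correlation differ, for example with subject and subject-by-day intercepts.
- **Before database lock:** confirm that the ERT SAP says the same.

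The cost is a few sentences in the protocol or the ERT SAP and no new data. The small downside is that the richer covariance may not converge, which is why the fallback should be named in advance.
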